Changing prompts to eating may be particularly important for modifying the dietary intake of young children who, unlike adolescents and adults, do not yet have the cognitive capacity to inhibit intake of highly palatable foods in favor of selecting food based on healthfulness.²¹ Therefore, the objective of this Collaborative Research pilot study is to conduct T2 translational research among low-income preschool children by developing an easily-implemented alternative approach to family-style dining in Head Start called Mealtime Matters, where teachers receive focused training on preschooler nutrition, appropriate portion sizes for preschool children, and responsive feeding strategies that promote children's self-regulation of eating. The feasibility and impact of Mealtime Matters will be tested with 72 children from up to 7 Head Start classrooms in Adrian, Michigan. We hypothesize that Mealtime Matters will be feasible and acceptable to teachers. Further, by reducing prompts to over-consume and empowering teachers to direct children to serve appropriate portion sizes, we will: 1. Increase the proportion of children consuming within an acceptable range of the recommended kilocalories (kcal) during meals at Head Start¹⁵ and 2. Increase the servings of fruits and vegetables children consume during meals at Head Start. Sustained engagement in these dietary behaviors can prevent excessive weight gain and obesity.²²

The specific aims of this trial are:

Aim 1: Examine the effect of Mealtime Matters on children's dietary intake during meals at Head Start.

Aim 2: Examine the effect of Mealtime Matters on teacher/child mealtime interactions at Head Start.

Aim 3: Determine the feasibility and acceptability of Mealtime Matters among Head Start teachers.

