Observational studies support the assertion that a meaningful proportion of low-income children overconsume when allowed to self-serve. The Institute of Medicine recommends that children in preschools participating in the Child and Adults Care Food program consume a median of 338 kilocalories (kcal) during lunch.¹⁵ However Schwartz, et al.¹⁵ observed that ~32% of children consumed >130% of the recommended energy during lunch at preschool. [name] has extended this research and identified that excessive energy intake during family-style dining is driven by overconsumption of energy-dense meat and grains (e.g., bread, pasta, rice), while fruit and vegetable intake is far below recommendations. In a sample of 243 Head Start children participating in a recent trial led by [name],²⁴ [name] determined that children with high energy consumption during lunch at Head Start ate approximately 4 times as much meat and 3 times as much grains as compared to children whose energy intake was in the recommended range. Fruit and vegetable intake, however, did not differ between high consumers and recommended consumers. Overall, children consumed only 1/3 of recommended fruit and 1/4 of recommended vegetable intake. These dietary patterns place children at high risk for obesity and obesity-related chronic disease.²²

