E.2. Children's dietary intake. Children's dietary intake will be measured at baseline and follow-up via the Remote Food Photography Method.^{28,30} Data will be collected during 3 lunch periods. Although all feeding occasions are targeted by the intervention, we will observe changes in lunch intake because children are served the most foods and expected to have the highest energy intake at lunch, providing the greatest potential for variability in intake between conditions.

The Remote Food Photography Method captures images of children's cups and plates before they eat (pre-intake) and after they eat (post-intake) each serving. The method was developed and has been extensively tested by [name], H. [name]., and colleagues. Staff will place a reference card next to each child's place setting and capture images pre- and post-consumption using a recording device such as an iPad, iPod, or GoPro that is not connected to the Internet. The images will then be saved and organized on a University of Michigan secure server. Once organized and stripped of any potential identifiable information, the images will be securely transferred to the Pennington Biomedical Research Center for data analysis. Head Start will provide nutritional information for every food and drink served during the observation period to match the images of children's food and drink with its exact energy and nutrient composition. The data analysis process relies on a computer program called the Food Photography Application©. The program allows the operator to identify a match for each food or drink from the recipes provided. The operator then uses the program to estimate portion size consumed by visually comparing participants' images to images of foods and drinks with a known portion size. This process relies on existing and validated methodology^{28,30,63,64} and produces data including children's energy intake, intake of specific foods and food groups, and macronutrient and micronutrient intake.

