E.4. Covariates. We will collect the following covariate data: (1) children's weight and height, measured using standardized protocols,⁶⁶ to calculate body mass index (BMI), (2) child birthdate, (3) child sex, (4) child race/ethnicity, (5) maternal education, (6) family income-to-needs ratio, and (7) child eating behavior.

E.5. Statistical analysis and sample size. After completion of the study, the data will be unblinded and analysis will be performed following the plan described below. Prior to conducting analyses, we will run descriptive statistics and transform skewed outcome variables as necessary. Analyses will be based on the intention to treat principle where all the randomized participants, including children who did not complete follow-up data collection, will be included in the analysis based on their randomized intervention group.

To examine the effect of Mealtime Matters on children's dietary intake, baseline comparability of the two groups will be assessed using t-tests for continuous sociodemographic variables and chi-square tests for categorical sociodemographic variables. Then we will employ logistic regression models using general estimating equation techniques accounting for classroom clustering of behavior to identify associations between study condition and binary outcomes (e.g., proportion of children consuming > 130% of recommended kcals). Multi-level linear regression models accounting for within-classroom clustering will be used to examine associations between study condition and continuous outcomes (e.g., servings of fruits and vegetables consumed). Analyses will be conducted unadjusted and adjusted for baseline characteristics including child age, sex, race/ethnicity, BMI, and baseline levels of the outcome. Similar analyses will be used to examine the impact of the intervention on teacher/child mealtime interactions.

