To determine the feasibility and acceptability of Mealtime Matters among Head Start teachers (**Aim 3**), we will use univariate statistics to describe teachers' quantitative responses to the survey and qualitative responses will be summarized by trained study staff to identify impactful and consistent themes. Teachers' quantitatively-coded behavior from the video recordings will also be described using univariate statistics. The research team will review the distributions of behaviors and responses from these sources and develop a summary report regarding the acceptability and feasibility of the intervention including reflections on areas for continued improvement.

We are interested in estimating effect sizes of the intervention for a future fully-powered efficacy trial. We do not anticipate that given our sample size, we will be able to detect significant differences between conditions at $p < .05$. However, assuming an intraclass correlation of 0.05 and 3 classrooms/condition with 10 students each, we will be able to detect an effect size of $0.79SD$ at $p < .05$.

E.6. Potential Challenges and Alternative Approaches. Collaborating with Head Start necessitates working within their academic year and being considerate of challenges facing the organization. Although we have a well-established relationship with Head Start, there is a chance that there will be too many competing priorities to begin recruitment. We have developed our timeline such that recruitment can begin in September 2018 and we can still complete the study protocol before the end of the academic year. If recruitment is not possible before September 2018, we will begin the trial in 2019 upon the start of the new school year. We also recognize that having research staff in Head Start classrooms may be distracting for children. To minimize this concern, research staff will conduct a run-in day of food photography during the baseline and follow-up periods. We will also run a quick pilot testing before data collection in order to refine the Remote Food Photography protocol; no identifying information or identifying pictures will be collected at this time. The presence of research staff is also equal across conditions, minimizing concerns of bias.

F. Study timeline

Feb 2018:	The Project Manager will develop and submit the study's IRB application.
April/May 2018:	Focus group session with teachers.

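### E.5 implies that the >130% energy outcome is adjusted for baseline yes/no status; naming the baseline lunch kcal already collected is a minor, free improvement

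*Combined protocol and SAP*

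**What the plan says.** Section E.5 analyses binary outcomes with "logistic regression models using general estimating equation techniques accounting for classroom clustering of behavior". Its one example of such an outcome is "binary outcomes (e.g., proportion of children consuming > 130% of recommended kcals". The adjustment rule that follows is common to binary and continuous outcomes: "Analyses will be conducted unadjusted and adjusted for baseline characteristics including child age, sex, race/ethnicity, BMI, and baseline levels of the outcome".

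Hypothesis 1 in Section A is a different binary energy outcome, with two limits: "Increase the proportion of children consuming within an acceptable range of the recommended kilocalories (kcal) during meals at Head Start". Neither limit is given.

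On data, Section E.2 states: "Children's dietary intake will be measured at baseline and follow-up via the Remote Food Photography Method". The method "produces data including children's energy intake, intake of specific foods and food groups, and macronutrient and micronutrient intake". So baseline kcal will exist for each child photographed at baseline. Neither the covariate list in E.4 nor the adjustment list in E.5 names it. The plan also does not say how the three lunches are combined into one yes/no value per child.

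**The concern.** If the outcome is whether a child exceeds 130% of the recommendation, its baseline level is most naturally whether the child exceeded it at baseline. That covariate treats a child just under the cut and a child far under it as alike, so it carries only part of the information in baseline kcal. Both forms use one coefficient.

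The study compares a handful of randomized classrooms, so some chance gap in baseline intake between the arms is to be expected. A covariate that captures intake only in part corrects such a gap only in part. E.5 says that significance is not expected and that the aim is to obtain effect estimates for planning a later trial. The point estimate is therefore the main product, and avoidable noise in it is worth removing when removal is free.

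**Working it through.** **Inputs from the documents.**
- Prevalence above the cut, p = 0.32, from the preschool study described in Section B: "32% of children consumed >130% of the recommended energy during lunch at preschool".
- Design, from E.5: "assuming an intraclass correlation of 0.05 and 3 classrooms/condition with 10 students each, we will be able to detect an effect size of" 0.79 SD.

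**Assumptions not in the documents.** Kcal is normally distributed. The correlation r between baseline and follow-up kcal is 0.4 to 0.7. There is one yes/no value per child per period. The treatment effect is null.

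**The plan's own figure.** The design effect is 1 + 9 × 0.05 = 1.45, so the effective size is 30/1.45 = 20.69 per arm. With 80% power, a two-sided t test gives a detectable effect of 0.893 SD and a one-sided one 0.787 SD; two-sided at 70% power gives 0.792 SD. The stated 0.79 SD therefore fits only with a sidedness or power that the plan does not state. It does not bear on this point; only the design inputs are used below.

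**Step 1: size of an ordinary chance gap.** The SD of the baseline gap between arms is sqrt(2/30 × 1.45) = 0.31 SD of kcal. With 72 children in 7 classrooms (Section A), the effective size is 24.59 per arm and the SD is sqrt(2/24.59) = 0.29. A gap of 0.3 SD is thus about one SD of what chance produces.

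**Step 2: what remains after adjustment, >130% outcome.** The cut is at c = 0.468, where the normal density is 0.358. On the risk-difference scale:
- false difference, unadjusted = r × 0.358 × 0.3
- b = (P11 − p²)/(p(1 − p)), the coefficient on baseline yes/no, where P11 is the bivariate normal probability of being above the cut both times
- share left after yes/no adjustment = 1 − b/r

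At r = 0.5, P11 = 0.172, so b = (0.1723 − 0.1024)/0.2176 = 0.321 and the share left is 1 − 0.321/0.5 = 0.36.

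| r | Unadjusted (points) | b | Share left | Left after yes/no (points) |
|---|---|---|---|---|
| 0.4 | 4.3 | 0.251 | 0.37 | 1.6 |
| 0.5 | 5.4 | 0.321 | 0.36 | 1.9 |
| 0.6 | 6.4 | 0.397 | 0.34 | 2.2 |
| 0.7 | 7.5 | 0.482 | 0.31 | 2.3 |

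Large simulations agree: at r = 0.5, 5.4 points unadjusted, 2.0 after yes/no and 0.1 after kcal. On the log-odds scale the share left is about 40% after yes/no and about zero after kcal. Widening to prevalence 20 to 50% and r 0.2 to 0.7 moves the risk-difference share to 29 to 47%.

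**Step 3: precision.** In 20,000 simulated trials of 3 v 3 classrooms of 10 at ICC 0.05, the SD of the adjusted risk difference (yes/no v kcal) was 0.1270 v 0.1247 at r = 0.5 and 0.1165 v 0.1132 at r = 0.7. The variance ratios are (0.1270/0.1247)² = 1.04 and (0.1165/0.1132)² = 1.06. Across r = 0.4 to 0.7 they run from 1.022 to 1.065.

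**Step 4: the within-range outcome.** Keep 32% above the range and r = 0.5, and assume 15%, 32% or 45% below it. With a normal density of 0.233 at the lower limit, the 15% case has an unadjusted false difference of 0.5 × (0.358 − 0.233) × 0.3 = 0.019, or 1.9 points. Yes/no adjustment leaves 73% of that, about 1.4 points. With 32% below, the two tails cancel and the effect is about zero. With 45% below it is about 0.6 points, of which 91% remains.

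Alternatives to yes/no for this outcome:
- Absolute distance from the middle of the range still leaves roughly 30 to 60% of the gap effect in the asymmetric cases.
- Kcal plus kcal squared leaves almost none at r = 0.4 to 0.6 and at most about 0.1 point at r = 0.7. Its variance is 0.98 to 0.99 of that with yes/no.
- Linear kcal alone gives no gain in precision (ratio 1.00 to 1.01).

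**The case against.** **The yes/no form is an inference.** This stands. E.5 never says yes/no, and its covariate list is open-ended. If the baseline level were, for example, the number of lunches over the cut, less of the gap would remain. But the literal reading is yes/no, kcal is not named anywhere as a covariate, and the same sentence settles the form in either case before the data are unblinded.

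**Randomization makes this chance error, not bias.** This also stands. Sections D.1 and F place randomization of classrooms after baseline collection, so the gap averages to zero, and in simulation the mean null effect is about zero under either covariate. A reader might infer that the planned analysis is biased, or that leftover bias and lost precision are two separate costs. The documents support neither. The 2 points are the error given one particular imbalance, and they are already part of the variance in Step 3. Against an SD of about 12.7 points at r = 0.5, 2 points is roughly one-sixth.

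**The gain is small in a pilot.** True: uncertainty from six or seven classrooms dwarfs a variance change of a few percent. What remains is that the gain costs nothing for the >130% outcome.

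**Scale.** The variance figures are for the risk difference. A logistic model reports an odds ratio conditional on its covariates, so standard errors of log odds ratios are not directly comparable between the two covariate choices.

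**Conclusion.** The point holds as a minor improvement. For the >130% outcome, at 32% prevalence and an assumed correlation of 0.4 to 0.7, adjusting for baseline yes/no leaves about a third of the effect of a chance kcal gap: about 2 points for a gap of 0.3 SD, against about none with continuous kcal. Averaged over randomizations the cost is about 2 to 6% extra variance.

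A reader might extend the one-third figure to hypothesis 1. That is not supported: the within-range outcome has two limits, its gap effect is smaller and can vanish, and its size depends on limits the plan does not give. The sizes rest on the stated assumptions, chiefly the correlation, for which the plan has no figure.

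**What to change.** In E.5, state that:
- models for the >130% outcome adjust for the child's mean baseline lunch kcal as a continuous covariate, in place of baseline yes/no status;
- models for the within-range outcome adjust for baseline kcal plus kcal squared, not for absolute distance from the recommendation.

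The first change uses the same number of coefficients and the second uses one more. The binary outcomes stay unchanged and no new data are needed.

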[name] and [name] will additionally provide support for development of Mealtime Matters and analysis and interpretation of data on teacher/child mealtime interactions. [name] is an expert on preschool children's hunger and satiety signals and [name] is an expert on early childhood education and training teachers to support children's nutritional and emotional needs.

D. Approach

D.1. Study overview.

We will first conduct two to three focus groups with Adrian Head Start teachers in spring 2018 to identify their knowledge and beliefs regarding feeding children. They will be compensated \$20 each for participation along with lunch. The information gathered will be used to inform the Mealtime Matters curriculum. Afterwards, the Mealtime Matters training will be finalized.

Next, an information session will be scheduled with teachers to invite them to participate in the study. Then, once classrooms elect to participate, recruitment will occur of children in the study classrooms. Parents of these children will complete an informed consent form and a brief study survey. In-classroom data collection will then occur in fall 2018. Once baseline data collection is complete, teachers in classrooms will be randomized to receive the Mealtime Matters training in either fall 2018 or in spring 2019 (delayed treatment). Teachers trained in fall 2018 will also receive 2 booster training sessions to enhance protocol adherence. Follow-up data collection in classrooms and with teachers will occur during November/December 2018. Data processing, analysis, results dissemination, and development of an NIH R01 application to test Mealtime Matters in a fully-scaled efficacy trial will then occur.

D.2. Study population, recruitment, and enrollment criteria. To be eligible for Head Start, children must be 3 or 4 years old by the beginning of the academic year, therefore children will be between 3 and 5 years old during study participation. Children's families must also have a household income near or below the federal poverty line. Approximately half (58%) of children in the Adrian Public School's Head Start program are non-Hispanic white, 25% are Hispanic/Latino, 15% are African American, and 2% are of another race/ethnicity or are of mixed race/ethnicity. In 2015, 20% of children were obese and 16% were overweight.

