Each Head Start classroom contains 17 children, therefore to achieve a sample size of 10 children per classroom or 60 children total, a consent rate of 59% is needed. In Co-I [name]'s Head Start-based intervention that had similar eligibility criteria, 64% of families provided consent for their child to participate in the study.²⁴ Therefore, achieving a consent rate of 59% is highly feasible.

Children whose parents do not consent to study participation or who are not eligible for study participation may still be exposed to the intervention. Further, these children may be recorded in video recordings of mealtimes, however, no child-level data will be coded for these children. This information will be provided in the enrollment packet sent to parents describing that children's teachers may get additional nutrition training and the process of videotaping meals. Parents will then have the option to inform the study team that they do not want their child participating in these activities. If a parent informs the study team that they do not wish for their child to participate in these activities, then the child will be placed somewhere that is not in sight of the video camera, or in a different classroom for the 3 recorded lunches.

D.3. Mealtimes Matter. Classrooms will receive extra training about children's nutrition and ways to promote children's healthy eating. The training will address the basics of preschooler nutrition, recommended portion sizes for preschoolers, and responsive feeding approaches. Responsive feeding is a child-centered approach to feeding where children are encouraged to be attuned to their hunger and satiety signals.⁶¹ For example, if a child declines a portion of the meat/meat alternative or grains, the teacher may respond to them, "How does your tummy feel? Would you like a piece of bread to help your tummy feel full?" Teaching children such approaches for recognizing hunger and satiety have proven effective at improving children's self-regulation of eating.⁶²

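### The logistic GEE for binary outcomes rests on 6 or 7 classrooms with no small-sample correction and no named main model, so its intervals would be too narrow

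*Combined protocol and SAP*

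**What the plan says.** Section E.5 analyses binary outcomes with "logistic regression models using general estimating equation techniques accounting for classroom clustering of behavior". The example given is the proportion of children eating more than 130% of recommended kcal. Continuous outcomes go to multilevel linear models. Of both it says: "Analyses will be conducted unadjusted and adjusted for baseline characteristics including child age, sex, race/ethnicity, BMI, and baseline levels of the outcome".

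The number of classrooms is small. The power statement in E.5 assumes "3 classrooms/condition with 10 students each", which makes 6. Section A says the intervention will be "tested with 72 children from up to 7 Head Start classrooms", and the timeline in F also allows up to seven. Section D.2 plans for 10 children per classroom and 60 in all.

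E.5 does not give a working correlation, a small-sample correction, a reference distribution, a coding for race/ethnicity, a fallback if a model fails to fit, or a statement of which version is the main one. It does say that the purpose is to estimate effect sizes for a later trial and that significance is not expected.

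**The concern.** A robust (sandwich) standard error estimates the between-classroom variance from the classrooms themselves. With 3 per arm it is biased downwards, and a normal reference distribution adds to the error. The adjusted version asks for more: with race/ethnicity in the four groups of D.2 it has more coefficients than there are classrooms, and one of those groups is expected to hold about one child.

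What is at stake is the estimate and interval carried into the next grant application. The first hypothesis in section A concerns a proportion, so the binary model is not peripheral. The plan would yield two estimates, each with an interval that overstates precision, and no rule for which one is carried forward. Adjusted and unadjusted odds ratios also target different quantities, so they cannot be swapped freely as planning inputs.

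**Working it through.** **The plan's own figure.** E.5 states: "we will be able to detect an effect size of $0.79SD$ at $p < .05". The design effect is 1 + (10 − 1) × 0.05 = 1.45. Then d = (1.645 + 0.842) × √(2 × 1.45/30) = 0.77, or 0.787 with a t distribution on about 39 df. So 0.79 reproduces as a one-sided test with 80% power; sidedness and power are not stated. The figure concerns a continuous outcome and does not bear on the binary model, except that it fixes 6 classrooms and an ICC of 0.05.

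**Inputs**
- Classrooms: 6 (E.5) or up to 7 (A, F).
- Children: 60 (D.2) or 72 (A).
- ICC: 0.05 (E.5).
- Outcome rate: about 32%, from the observational study cited in B, which gives 0.32 × 60 = 19 or 0.32 × 72 = 23 events.
- Race/ethnicity: 58% non-Hispanic white, then "25% are Hispanic/Latino, 15% are African American, and 2% are of another race/ethnicity or are of mixed race/ethnicity" (D.2).

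**Why the standard error is too small.** Take the unadjusted model with equal classrooms. In an arm of k classrooms, the sandwich divides the squared deviations of classroom means by k² where an unbiased estimate divides by k(k − 1). With k = 3 the variance is 2/3 of what it should be and the SE is √(2/3) = 0.816 of it.
- Normal cutoff: rejection occurs when |t| on 4 df exceeds 1.96 × 0.816 = 1.60, probability about 18%.
- 4-df cutoff: 2.776 × 0.816 = 2.27, probability about 9%.
- Seven classrooms split 4 v 3: the variance ratio is (3/16 + 2/9)/(1/4 + 1/3) = 0.70, the cutoff is 1.96 × 0.838 = 1.64, and the probability on 5 df is about 16%.

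**Simulation under no effect.** Settings: exchangeable logistic GEE, uncorrected robust SE, latent-scale ICC 0.05, 300–400 data sets per setting. Results at a 32% outcome rate:

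| Rooms × children | Race groups | Adjusted model fails | Adjusted, z | Adjusted, K − 2 df | Unadjusted, z |
|---|---|---|---|---|---|
| 6 × 10 | 4 | 53% | 21% | 12% | 19% |
| 6 × 10 | 3 | 7% | 20% | 10% | 17% |
| 6 × 10 | 2 | 0% | 22% | 13% | 19% |
| 6 × 12 | 4 | 55% | 17% | 9% | 16% |
| 6 × 12 | 2 | 0% | 22% | 11% | 16% |
| 7 × 10 | 4 | 59% | 27% | 17% | 17% |
| 7 × 10 | 3 | 2% | 23% | 13% | 19% |
| 7 × 10 | 2 | 0% | 23% | 13% | 17% |

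Rejection rates are among data sets that fitted. With outcome rates from 20% to 50% included, the adjusted z-test rejects in 17–27% and the adjusted test on K − 2 df in 8–18%. The unadjusted z-test rejects in 14–19%, and a further simulation reached 22%. Failure covers 49–66% with four groups, 2–19% with three (rates of 20% and 32% only) and 0–3% with two.

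**Coefficients and rank.** Intercept 1 + condition 1 + age 1 + sex 1 + race/ethnicity 3 + BMI 1 + baseline outcome 1 = 9; with three groups 8, with two groups 7. Classroom score vectors sum to zero, so the robust covariance has rank at most K − 1: 5 or 6.

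**Source of the fit failures.** The 2% group is expected to hold 0.02 × 60 = 1.2 children (1.4 of 72). In 250 further data sets (6 × 10, 32%), 132 were separated, and 121 of those ceased to be once that group was removed. The software still returned a finite condition coefficient and SE in 57 of the 132, so a failure can go unnoticed.

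**Alternatives.** A two-stage classroom-level test adjusted for the baseline outcome rejected in 4.7% (6 rooms) and 5.3% (7 rooms), and in about 5–6% in another simulation. The adjusted GEE with a Mancl-DeRouen SE, at 6 × 10, rejected by z in 4.2% (three race groups) and 4.7% (two), and in 1–2% on 4 df.

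**The case against.** The strongest reply is that this is a pilot. E.5 says it aims to estimate effect sizes and does not expect significance, so false-positive rates are not its operating characteristic. That lowers the severity. It does not remove the point, because the same error that inflates rejection narrows the interval around the effect size.

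A reader might infer that the adjusted model has nine coefficients and often cannot be fitted because there are too few classrooms. The documents do not support this. D.2 describes the programme's population and does not say how race/ethnicity enters the model. Failure comes mainly from the 2% group and nearly disappears with two groups. Even the four-group figure is soft. A simulation that counted unusable output gave 29%. Another with each of the three lunches as its own record, which the plan does not rule out, reduced failure from 57% to 19%.

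A reader might also infer that rank deficiency makes the adjusted error bars invalid beyond repair. It rules out a joint Wald test of all coefficients. It does not block a standard error for condition, and a standard correction restores roughly the right rejection rate. Most of the inflation is shared with the unadjusted model.

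Finally, the plan commits to running both versions. Choosing between them after seeing the data is a risk that the plan leaves open, not something it proposes.

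**Conclusion.** The point holds for binary outcomes, as a should-fix. If the GEE is run with uncorrected robust SEs and normal reference values, both versions give intervals that are too narrow: false-positive rates are about 14–22% unadjusted and 17–27% adjusted against a nominal 5%. The plan names neither as the main estimate. Separation is a second and conditional problem: roughly half of data sets with four race/ethnicity groups, about 2–19% with three and 0–3% with two.

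The documents do not support the stronger reading that the adjusted GEE must be dropped. Continuous outcomes, including fruit and vegetable servings, use a different model and are outside this point.

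The figures assume an ICC of 0.05 and an outcome rate of about 32%. That rate comes from an outside sample and applies to the more-than-130% example; none is given for intake within an acceptable range. Assumptions not in the documents are an exchangeable working correlation, equal classroom sizes, one binary value per child, covariates unrelated to outcome, a moderate baseline-to-follow-up correlation and no dropout. Monte Carlo error is about 2 percentage points, √(0.2 × 0.8/400), and somewhat more for the four-group adjusted rates, where fewer data sets fitted.

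**What to change.** In E.5, for binary outcomes:

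1. Name one main estimate, adjusted for the baseline value of the outcome.
2. Use inference suited to few classrooms, by one of two routes. (a) Two stages: regress each child's follow-up value on the baseline value without a condition term, then compare classroom mean residuals between conditions with a t-test on classrooms minus 2 df. (b) Keep the GEE with a Mancl-DeRouen type corrected SE and state the reference distribution in advance. The results above for this route are for the full covariate set with collapsed race/ethnicity, so the baseline-only version should be checked by simulation first.
3. Report adjustment for age, sex, BMI and collapsed race/ethnicity as a sensitivity analysis, with the grouping fixed in advance and a fallback stated if the model is separated or does not converge.

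The cost is SAP wording and no new data. Intervals will be wider: at a given SE, moving from 1.96 to the t cutoff multiplies the width by 2.776/1.96 = 1.42 with 6 classrooms, or 2.571/1.96 = 1.31 with 7. Route (a) gives risk differences instead of odds ratios. Chance imbalance in BMI or race/ethnicity is addressed only in the sensitivity analysis. The timeline in F places analysis in February 2019; if the data have already been analysed, the change should be reported as made afterwards.
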